10.2.4 Other continuous secondary efficacy endpoints

Following continuous endpoints will be analyzed using an analysis of covariance (ANCOVA) model, with treatment as a fixed effect and baseline WHO Ordinal Scale score, age group (50 to < 75 vs. ≥ 75 years of age) and region. Results from Wilcoxon rank sum test and t-tests will also be reported. The ITT and PP analysis (if formed) sets will be used for these exploratory subset analyses.

- Duration of intubation: which will be defined as duration of first post-dosing intubation based on start and end date of the intubation.

QMS Document Name: Statistical Analysis Plan	Page 21 of 27
QMS No (include version ref): STF-015-GL.02	Document date: 09JUL2019
CONFIDENTIAL	

- Length of intensive care unit (ICU) stay in days which will be defined as duration of first post-dosing ICU stay based on start and end date/time of the stay.
- Duration of supplemental O₂ administration in days : which will be defined as duration of first post-dosing supplemental O₂ administration based on start and end date/ of the O₂ administration.
- Duration of noninvasive ventilation or high-flow oxygen therapy in days: which will be defined as duration of first post-dosing noninvasive ventilation or high-flow oxygen therapy based on start and end date/time of the noninvasive ventilation or high-flow oxygen therapy.
- Duration of mechanical ventilation in days: which will be defined as duration of first post-dosing mechanical ventilation based on start and end date/time of the mechanical ventilation.
- Duration of mechanical ventilation plus additional organ support using vasopressors, and/or renal replacement therapy and/or ECMO: which will be defined as duration of first post-dosing mechanical ventilation plus additional organ support using vasopressors, and/or renal replacement therapy and/or ECMO based on start and end date/time of the mechanical ventilation plus additional organ support using vasopressors, and/or renal replacement therapy and/or ECMO.
- Daily ratio of oxygen saturation (SpO₂) to fractional inspired O₂ (SpO₂/FiO₂): which will be defined as SpO₂/FiO₂ as collected in CRF. The ratio will be analyzed for each day with the value being collected. If FiO₂ was not collected for some O₂ delivery methods, following guide can be followed to convert O₂ flow rate to FiO₂.

O ₂ delivery method	O ₂ flow rate (l/min)	Estimated FiO ₂
Nasal cannula ("NASAL CANNULA LARGE TUBING" and "NASAL CANNULA TRADITIONAL TUBING")	1	24
	2	28

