	3	32
	4	36
	5	40
	>=6	44
Nasopharyngeal catheter	1	25
	2	30
	3	35
	4	40
	5	50
	>=6	60
Face mask (simple mask)	<5	Follow nasal cannula
	5	40
	6-<7	50
	>=7	60

Face mask with reservoir (non-rebreather face mask)	<6	Follow nasal cannula
	6	60
	7	70
	8	80
	9	90
	10	95
	>10	100
Venturi mask	1	22
	2	24
	3	26
	4	28
	6	31
	8	40
	10	50
	>10	60

In case of fractional value of flow rate (0.5, 1.5, 2.5, 3.5, 4.5), $\text{FiO}_2 = (\text{Oxygen Flow Rate} * 4) + 20$ to avoid rounding.

- Length of hospital stay, after start of study treatment, in days: which will be defined as duration from date of randomization to the date of first discharge.

11 Safety

All safety endpoints will be analyzed using the SAF under received treatment based on the data observed. No missing data will be imputed.

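### The FiO2 formula for fractional oxygen flows in SAP 10.2.4 has no device limit and contradicts the SAP's own nasopharyngeal catheter and Venturi mask rows

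*SAP*

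**What the plan says.** Secondary endpoint 15 is the daily SpO2/FiO2 ratio. SAP 10.2.4 says of it: "The ratio will be analyzed for each day with the value being collected". Where FiO2 was not collected for a delivery method, the "following guide can be followed to convert O₂ flow rate to FiO₂". The guide is a table for five methods:

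- nasal cannula (including "NASAL CANNULA TRADITIONAL TUBING");
- "Nasopharyngeal catheter";
- simple face mask;
- face mask with reservoir;
- Venturi mask.

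The simple mask below 5 L/min and the reservoir mask below 6 L/min carry the entry "Follow nasal cannula".

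One sentence stands under the whole table, after the Venturi rows. It begins "In case of fractional value of flow rate (0.5, 1.5, 2.5, 3.5, 4.5") and sets FiO2 to 4 × flow + 20 "to avoid rounding". It names no device and makes no exception.

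Protocol 7.2.6 takes FiO2 from the device when there is a readout. Otherwise the site records the delivery method and flow, and the Sponsor derives the ratio by accepted standards. That does not restrict the formula to particular devices, and SAP 1 says the SAP prevails if the two documents differ.

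**The concern.** A programmer who follows the sentence literally applies one line to all five delivery methods. That line is the nasal cannula scale. The catheter table rises faster with flow and the Venturi table more slowly, so half-litre flows on those devices fall out of step with the whole-litre flows on either side.

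For some steps, estimated FiO2 then moves the wrong way as flow rises. A catheter patient going from 4 to 4.5 L/min would show a better SpO2/FiO2 ratio on more oxygen at the same saturation. A Venturi patient going from 3 to 3.5 to 4 L/min would show a sharp fall and then a recovery. The error is upward for one device and downward for the other, so it is not a constant offset. What is at stake is the accuracy of individual daily values in endpoint 15, which SAP 10.2.4 analyses by ANCOVA, Wilcoxon test and t-test.

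**Working it through.** **Inputs (SAP 10.2.4; FiO2 in %).**
- Formula: FiO2 = 4 × flow + 20, at 0.5, 1.5, 2.5, 3.5 and 4.5 L/min.
- Cannula: 24, 28, 32, 36, 40 at 1 to 5 L/min; 44 at 6 or more.
- Catheter: 25, 30, 35, 40, 50 at 1 to 5 L/min; 60 at 6 or more.
- Venturi: 22, 24, 26, 28 at 1 to 4 L/min; 31 at 6, 40 at 8, 50 at 10; 60 above 10.
- SpO2 of 94% is my assumption, for illustration. It cancels from the percentage errors below.

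**Step 1: which rows does the formula reproduce?** At 1, 2, 3, 4, 5 and 6 L/min it gives 24, 28, 32, 36, 40 and 44, exactly the cannula rows. Every listed fractional flow is 4.5 or lower, so it also fits both masks where they follow the cannula. At whole-litre flows it differs from the catheter table by −1, −2, −3, −4 and −10 points (1 to 5 L/min). It differs from the Venturi table by +2, +4, +6 and +8 points (1 to 4 L/min) and by +13 at 6 L/min.

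**Step 2: does each fractional value lie between its tabled neighbours?** This uses only the SAP's own numbers.

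| Flow (L/min) | Formula | Catheter neighbours | Catheter result | Venturi neighbours | Venturi result |
|---|---|---|---|---|---|
| 0.5 | 22 | none below; 25 at 1 | no conflict | none below; 22 at 1 | ties with value at 1 |
| 1.5 | 26 | 25 to 30 | inside | 22 to 24 | too high |
| 2.5 | 30 | 30 to 35 | ties with value at 2 | 24 to 26 | too high, also above 28 at 4 |
| 3.5 | 34 | 35 to 40 | too low | 26 to 28 | too high, also above 31 at 6 |
| 4.5 | 38 | 40 to 50 | too low | 28 (at 4) to 31 (at 6) | too high |

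**Step 3: size against interpolation.** Linear interpolation within each device's table is a benchmark of my choosing; the SAP does not define it as correct. For Venturi at 4.5 L/min it gives 28 + (0.5/2) × (31 − 28) = 28.75. SpO2/FiO2 is 9400 divided by FiO2 in %. The error in the ratio is interpolated FiO2 / formula FiO2 − 1.

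| Device, flow | Formula FiO2 | Interpolated FiO2 | Ratio by formula | Ratio by interpolation | Error in ratio |
|---|---|---|---|---|---|
| Catheter 1.5 | 26 | 27.5 | 361.5 | 341.8 | +5.8% |
| Catheter 2.5 | 30 | 32.5 | 313.3 | 289.2 | +8.3% |
| Catheter 3.5 | 34 | 37.5 | 276.5 | 250.7 | +10.3% |
| Catheter 4.5 | 38 | 45 | 247.4 | 208.9 | +18.4% |
| Venturi 1.5 | 26 | 23 | 361.5 | 408.7 | −11.5% |
| Venturi 2.5 | 30 | 25 | 313.3 | 376.0 | −16.7% |
| Venturi 3.5 | 34 | 27 | 276.5 | 348.1 | −20.6% |
| Venturi 4.5 | 38 | 28.75 | 247.4 | 327.0 | −24.3% |

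**Step 4: the jumps at SpO2 94%.** Catheter 4 to 4.5 L/min: 9400/40 = 235.0 rises to 247.4. Venturi 3, 3.5, 4 L/min: 9400/26 = 361.5, then 276.5, then 9400/28 = 335.7.

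**Step 5: table gap.** The Venturi rows have no entry for 5, 7 or 9 L/min, and the fractional-flow sentence does not cover whole-litre flows.

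**The case against.** The strongest reply is that the sentence was meant for the cannula scale only. The formula equals the cannula rows exactly, and its list stops at 4.5, just under the flow at which the simple mask leaves those rows. On that reading this is missing scope wording rather than a wrong formula. The table is also worded permissively ("following guide can be followed to convert") and is used only where FiO2 was not collected. The intention is plausible, but the text does not state it and nothing elsewhere supplies it. Followed as written, the rule gives values that the table above it contradicts.

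The reply on consequence is stronger, and most of it stands. The same rule applies in both blinded arms. Endpoint 15 is one of 18 secondary endpoints, Protocol 8.4 designates none as key, and SAP 10.2 makes no multiplicity adjustment.

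A reader might infer more than the documents support:
- **That the treatment comparison is biased.** Device and flow arise after randomisation, so balance between arms is not guaranteed. But no imbalance is shown and the number of affected records is not given.
- **That Venturi records at 5, 7 or 9 L/min are lost.** The SAP gives no value for those flows, but does not say the records are dropped.
- **That the SpO2/FiO2 summaries among the vital signs carry the same error.** SAP 11.3 lists the ratio but does not say this guide feeds it.

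**Conclusion.** The point holds as an internal contradiction in SAP 10.2.4, confined to two of five delivery methods. It is certain for catheter flows of 3.5 and 4.5 L/min and Venturi flows of 1.5 to 4.5 L/min, because it rests only on the SAP's tables and formula. Catheter 1.5 and 2.5 L/min do not contradict the table, though both fall below the interpolated value.

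The size, about 6% to 18% too high for the catheter and 12% to 24% too low for Venturi over 1.5 to 4.5 L/min, depends on taking linear interpolation as the benchmark. It applies per affected record, not to an arm mean. A record is affected only if FiO2 was not collected, the device is a catheter or Venturi mask, and the flow is one of those listed. Any effect on the treatment comparison in endpoint 15 therefore cannot be quantified. The primary endpoint does not use this conversion. The correction is worth making because the rule is wrong as written and costs almost nothing to put right.

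**What to change.** In SAP 10.2.4:

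1. Limit the fractional-flow formula to nasal cannula, and to the simple mask (below 5 L/min) and reservoir mask (below 6 L/min) rows that follow it.
2. For catheter and Venturi mask, interpolate linearly between tabled flows. This also supplies the missing Venturi values: (28 + 31)/2 = 29.5 at 5 L/min, (31 + 40)/2 = 35.5 at 7 and (40 + 50)/2 = 45 at 9.
3. State a rule for 0.5 L/min on those two devices. It lies below their first tabled flow, so interpolation cannot supply it. One option is to carry the 1 L/min value (25% catheter, 22% Venturi).

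The cost is a sentence or two in the SAP and a small program change, with no new data. Protocol 7.2.6 already has sites record delivery method and flow when there is no FiO2 readout, so affected records can be counted without treatment codes and the count reported with the change.

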### **8.3 Data Handling**

Data that may potentially unblind the treatment assignment (e.g., IP serum concentrations, treatment allocation, and IP preparation/accountability data) will be handled with special care during the data cleaning and review process. Unless otherwise specified, these data will be handled in such a way that, prior to unblinding, any data that may unblind study team personnel will be presented as blinded information or otherwise will not be made available. If applicable, unblinded data may be made available to quality assurance representatives for the purposes of conducting independent drug audits.

All analyses/summaries will be based on observed data, with no imputation for missing data, unless otherwise specified in the statistical analysis plan (SAP).

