10.2 Secondary efficacy analyses

All secondary efficacy endpoints will be analyzed without adjustment for multiplicity using ITT and mITT and PPS (if formed) under randomized treatment based on the data observed. No missing data will be imputed unless specified otherwise.

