- Incidence of mechanical ventilation plus additional organ support using vasopressors, and/or renal replacement therapy and/or ECMO: which will be defined as proportion of patients who had any documented post-dosing mechanical ventilation plus additional organ support using vasopressors, and/or renal replacement therapy and/or ECMO.

QMS Document Name: Statistical Analysis Plan	Page 20 of 27
QMS No (include version ref): STF-015-GL.02	Document date: 09JUL2019
CONFIDENTIAL	

- Incidence of re-hospitalization through Day 57: which will be defined as proportion of patients who are hospitalized again after the discharge of first hospitalization.

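### Length of hospital stay has no value for patients who die in hospital or are never discharged, so the nominal ITT comparison covers only patients discharged at least once and can favour the arm with more deaths

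*SAP*

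**What the plan says.** SAP 10.2.4 lists length of hospital stay among the continuous secondary endpoints and measures it in days, "which will be defined as duration from date of randomization to the date of first discharge". For the whole group, "Following continuous endpoints will be analyzed using an analysis of covariance (ANCOVA) model", with treatment, baseline WHO score, age group and region in the model. "Results from Wilcoxon rank sum test and t-tests will also be reported". On populations it says: "The ITT and PP analysis (if formed) sets will be used for these exploratory subset analyses".

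SAP 10.2 has all secondary efficacy endpoints analysed "under randomized treatment based on the data observed. No missing data will be imputed unless specified otherwise". Protocol 8.3 agrees: "All analyses/summaries will be based on observed data, with no imputation for missing data, unless otherwise specified" in the SAP.

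Re-hospitalisation through Day 57 (SAP 10.2.1) is the "proportion of patients who are hospitalized again after the discharge of first hospitalization". Unless stated otherwise, SAP 4.1 takes the whole analysis set as the denominator for percentages.

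Neither document says what length of stay is given to a patient who dies before any discharge, or who is still in hospital when follow-up ends.

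**The concern.** A duration that ends at discharge exists only for patients who are discharged. Whether a patient is discharged or dies first is decided after randomisation and is something the treatment is meant to change, since death is part of the primary endpoint. Comparing stay only among those with a value therefore compares groups that randomisation did not form. If one arm loses more of its sickest patients to death, its remaining patients are on average the faster recoverers, and its mean stay looks shorter for the wrong reason. The result would carry an ITT label, a confidence interval and a p-value, and a reader could not undo the selection from the survival table.

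Re-hospitalisation has a related weakness. A patient who dies before discharge stays in the denominator and counts as not re-hospitalised, which is scored as the good outcome.

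**Working it through.** **1. The plan's own figure.** No figure is stated for length of stay. The one design figure is the total of 312 for the primary endpoint (31% against 15%, two-sided 5%, 90% power). Only the arm size is needed from it. With a mean proportion of 0.23, n = [1.960·√(2×0.23×0.77) + 1.282·√(0.31×0.69 + 0.15×0.85)]² / 0.16² = 143.3. The continuity correction (143.3/4)·[1 + √(1 + 4/(143.3×0.16))]² gives 155.5, so 156 per arm and 312 in total, as stated.

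**2. Who has a value under the SAP definition.**

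| Patient | First discharge date | Enters the comparison |
|---|---|---|
| Discharged alive | yes | yes |
| Discharged, dies later | yes | yes |
| Dies before any discharge | no | no |
| Alive, never discharged during follow-up | no | no |

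**3. Rules that might fill the gap.** SAP 4.4 carries deaths forward to Day 28, but only for WHO scores. SAP 10.2.2 censors deaths at Day 28, but only for time to clinical improvement. The date rules in SAP 4.4 complete missing parts of dates of events that happened. They do not supply a date for a discharge that never took place. None covers length of stay.

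**4. Size in an assumed case.** All inputs here are assumptions.
- Stay is log-normal with median M and log-SD σ.
- Death falls on the fraction d with the highest risk score.
- The risk score has correlation ρ with log stay.
- Treatment has no effect on stay.

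Mean stay among those discharged is then M·exp(σ²/2)·Φ(c − σρ)/(1 − d), where c is the (1 − d) normal quantile.

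With M = 8, σ = 0.6 and ρ = 0.82, M·exp(σ²/2) = 9.58 and σρ = 0.49:
- d = 10%: 9.58 × Φ(1.28 − 0.49)/0.90 = 9.58 × 0.785/0.90 = 8.36 days
- d = 5%: 9.58 × Φ(1.64 − 0.49)/0.95 = 9.58 × 0.876/0.95 = 8.83 days
- difference: −0.47 day, favouring the arm with more deaths

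At the same median and 10% against 5%:
- σ = 0.5, ρ = 0.5: 8.55 against 8.76, a gap of 0.21 day
- σ = 0.6, ρ = 1.0: 8.01 against 8.59, a gap of 0.58 day

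The gap scales with the median, so at 9 days the largest becomes 0.58 × 9/8 = 0.65.

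**5. Effect on the test.** This is a simulation of 1,500 trials per scenario at 156 per arm, with M = 8, σ = 0.6 and no effect on stay. The last two columns give the percentage of trials with a significant Wilcoxon result in favour of the arm with more deaths.

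| Deaths | Mean difference, discharged only (days) | Discharged only | Death as worst rank |
|---|---|---|---|
| 10% v 5% | −0.47 | 10.7% | 1.1% |
| 15% v 5% | −0.84 | 24.0% | 0.7% |
| 20% v 10% | −0.73 | 23.8% | 0.1% |
| 15% v 5%, deaths unrelated to stay | +0.02 | 2.7% | 0.0% |

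With 5% deaths in both arms the mean difference was 0.00 day, and 3.9% and 4.3% of trials were significant in the two directions. The simulation assigned deaths to the highest-risk patients within each arm, which makes the test slightly liberal. The first three rows should therefore be read against about 4%, not 2.5%.

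**6. If sites enter the date of death as the discharge date.** With an assumed median of 10 days to death, the first three scenarios give 6.1%, 11.3% and 7.8% in favour of the arm with more deaths. When deaths are unrelated to stay, the shift is +0.19 day against that arm. This reading does not remove the problem, and its direction depends on how quickly patients die.

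**The case against.** The SAP never says that deaths are excluded. It is silent, and the table, figure and listing specifications are in a separate document that may contain a rule. That stands as a limit on how firmly the point can be put. But the definition and the observed-data rule, followed as written, do leave these patients out.

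The consequence is limited, and this also stands. No secondary endpoint is designated key, none is corrected for multiplicity, and SAP 10.2.4 itself calls these analyses exploratory. The interim rule uses only the primary endpoint. Deaths are visible in the primary composite, in survival at Days 14, 28 and 57, and in the safety tables. With an assumed SD of about 6 days, the standard error of a difference at 156 per arm is 6 × √(2/156) = 0.68 day, so a shift of 0.47 day is less than one standard error. The SAP addendum says enrolment stopped before the interim analysis. The documents do not give the number enrolled, and smaller arms would bring the rejection rates closer to nominal.

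Three stronger readings are tempting and not supported:
- A reader might infer that the comparison is restricted to survivors. It is restricted to patients discharged at least once: later deaths are in, and living patients never discharged are out.
- A reader might infer that proper handling of deaths reverses the sign. Scoring each death as 28 days does so in step 4: 0.90 × 8.36 + 0.10 × 28 = 10.32 against 0.95 × 8.83 + 0.05 × 28 = 9.79. But reversal needs a death score above (0.95 × 8.83 − 0.90 × 8.36)/0.05, about 17 days (about 16 at ρ = 0.7). The reversed figure also mixes mortality into the score, so it answers a different question and is not a corrected stay.
- A reader might infer that re-hospitalisation should be compared among patients discharged alive. That repeats the same post-randomisation selection. The SAP's all-randomised denominator is the better basis.

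**Conclusion.** The point holds. As written, the stay comparison leaves out in-hospital deaths and never-discharged patients while being labelled ITT, and it can favour the arm with more deaths. Two conditions are needed: unequal deaths, and deaths concentrated in patients who would have stayed longer. Without either one there is no bias.

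The documents support no firm size, because they give neither a death rate nor a stay distribution. Under the assumed 10% against 5% deaths and a median stay of 8 days, the shift is about 0.2 to 0.6 day, with some inflation of the Wilcoxon test. The priority is modest: it affects how one non-key secondary result is read, not the trial's conclusion.

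**What to change.** - Keep length of stay among discharged patients as a descriptive summary, and show by arm the numbers who died in hospital and who were never discharged.
- Base the between-arm comparison on all randomised patients. Either use a Wilcoxon test with in-hospital death as the worst rank and never-discharged patients ranked just below it, or use hospital-free days to Day 28 with death scored as 0. Name one in advance. For hospital-free days, also state how readmission days count.
- For re-hospitalisation, keep the all-randomised denominator and add a composite of death or re-hospitalisation through Day 57. Do not use patients discharged alive as the comparative denominator.

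The cost is a short SAP change and one derived variable, from death and discharge data that existing endpoints already need. The endpoint named in the protocol stays in place. The drawback is that the new comparison combines mortality with stay and must be labelled so. If the change comes after unblinding, it should be reported as post hoc.

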11.1 Adverse events

Adverse events will be coded using MedDRA version 23.1 and will be graded according to the NCI-CTCAE version 5.0. AE summaries will be presented by primary SOC and PT.

Treatment-emergent Adverse events will be considered as any event or worsening of event with onset on or after receiving the first dose of study drug through Day 57.

Summaries will be presented by actual treatment and overall using the SAF. Although a PT or SOC may be reported more than once for a patient, each patient will only be counted once.

Number and frequencies of patients with TEAEs as well as number of events will be given by SOC and by PT within each SOC for the following:

- All TEAEs by treatment group
- Serious TEAEs by treatment group
- All TEAEs considered related by treatment group
- Serious TEAEs considered related by treatment group

QMS Document Name: Statistical Analysis Plan	Page 23 of 27
QMS No (include version ref): STF-015-GL.02	Document date: 09JUL2019
CONFIDENTIAL	

- All TEAEs by maximum severity and by treatment group
- TEAEs leading to death by treatment group
- TEAEs leading to study discontinuation of study drug by treatment group

Additionally, number and frequencies of patients with TEAEs as well as number of events will be presented by decreasing frequency for all TEAEs, serious TEAEs and TEAEs considered at least possibly related.

If severity is missing, the event will be graded as severe unless the event being recorded is leading to life-threatening or death and will be graded accordingly as grade 4 (life-threatening) or 5 (death). If relationship to study drug is missing, the event will be assessed as unrelated if it started before start of IMP; in all other cases it will be assumed to be related.

Patient listings will be provided for patients with adverse events, treatment emergent adverse events, serious adverse events, for all patients with adverse events leading to withdrawal of IMP, and for all adverse events leading to death.

